radiographic findings, and TB testing in line with local practice), hepatitis B (known positive HBV surface antigen (HBsAg) result), hepatitis C. Patients with a past or resolved HBV infection (defined as the presence of hepatitis B core antibody [anti-HBc] and absence of HBsAg) are eligible. Patients positive for hepatitis C (HCV) antibody are eligible only if polymerase chain reaction is negative for HCV RNA.

9. Body weight < 30 kg

Specific to Consolidation Therapy

1. Patients must have recovered from toxicities associated with prior chemoradiation to CTCAE < Grade 2.
2. Patients must not have progressed following chemoradiation therapy, as measured on imaging per RECIST 1.1.
3. Confirmation of ECOG Performance Status of 0 or 1.
4. Any grade pneumonitis from prior chemoradiation will not be permitted.

[figure not shown]
STATISTICAL CONSIDERATIONS	
In the PACIFIC study, 12-month progression-free survival was 55.9% (1).
 
This study will be planned to detect a 14% improvement in 12month progression-free survival as a potential signal to move forward with further evaluation in a large randomized trial. Thus, 12-month progression-free survival of 69.9% would be felt to be clinically meaningful for further investigation.
 
Assuming that 12-month PFS in the historical control group is 55.9%, with an 18-month accrual interval and additional 12month follow up after the accrual interval, the required sample size would be 49 patients, with a one-sided test given type I error 0.05 and power of 0.8.
 
Accounting for a 10% dropout rate, a total of 54 patients would be enrolled in this study.

TOTAL NUMBER OF SUBJECTS	N = 54
ESTIMATED ENROLLMENT PERIOD	Estimated 18 months
ESTIMATED STUDY DURATION	Estimated 36 months

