## 7. STUDY CALENDAR & EVALUATIONS

Induction and Consolidation: Cycle = 28 days	Screen	Induction	Chemoradiation	Consolidation	Safety follow up visit 	Long-term Follow up 
	-28 days	Cycle 1		Day 1 ± 3	Cycle 1-12	Every 3 months (±14days)
		Day 1 ± 3				
REQUIRED ASSESSMENTS						
Informed Consent	X					
Medical History 	X					
Diagnosis and Staging 	X					
Physical Exam 	X	X	X 3	X	D30	
Vital signs and ECOG Performance Status 	X	X	X 3	X	D30	
ECG	X					
AEs & concomitant medications	X	X	X 3	X	X	
LABORATORY ASSESSMENTS						
Complete Blood Cell Count with diff (CBC)	X	X 13	X	X	D30	
Comprehensive Metabolic Profile (CMP)	X	X 13	X	X	D30	
PT/INR and aPTT	X					
Thyroid Function Testing 	X			X 5		
Pregnancy test (serum or urine) (WOCBP) 	X	X 6		X 6		
DISEASE ASSESSMENT						
CT of chest 	X			X 7	X 7	X 7
CT or MRI of abdomen and pelvis 				X 7	X 7	X 7
MRI or CT Brain 	X			as clinically indicated		
PET Scan 	X 7			as clinically indicated		

TREATMENT EXPOSURE						
Durvalumab		X		X		
Chemoradiation per standard of care			X			
SPECIMEN COLLECTION						
Archival Tumor Tissue 	X					
Blood Samples 		C1D1		X 9		
Stool Microbiome 		X 10				
FOLLOW-UP						
Survival Status, Subsequent Therapy						X

Key to Footnotes

1: Medical History; other data to be obtained during this assessment includes: (1) a smoking history questionnaire, (2) trial awareness question (3) documentation of prior anti-cancer treatment including medications (chemotherapy, checkpoint inhibitors, etc) radiation or surgery and (4) If prior genetic testing has been done those results should be made available.

2: Diagnosis and Staging to include pathology report and staging documentation. AJCC version 8 will be used for recording of staging.

3: Patients should have weekly physical exam and vital signs per good medical practice during chemoradiation. AEs and concomitant meds should be recorded weekly during chemoradiation.

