4: Vital signs to include temperature, pulse, respirations, blood pressure, weight, and height (screening only) and ECOG performance status. Patients will be monitored before, during and after the durvalumab infusion with assessment of vital signs. Patients are monitored (pulse rate, blood pressure) every 30 minutes (- 5 minutes/+ 10 minutes), during the infusion period (including times where infusion rate is slowed or temporarily stopped).

5: CBC with differential and platelet to include: WBC, ANC, Hgb, Hct, PLT. CMP to include sodium, potassium, chloride, creatinine, blood urea nitrogen; liver function tests (LFTs) to include AST, ALT, total bilirubin, alkaline phosphatase. Thyroid Function testing should be performed at

screening, at start of consolidation durvalumab, then every 3 cycles during consolidation durvalumab. TSH will be obtained. T4 and T3 including free versus total testing is at the discretion of the site investigator.

6: For women of childbearing potential (WOCBP): urine or serum  $\beta$ hCG will be done at screening and within 24 hrs of 1st dose of study drug. During treatment with consolidation durvalumab, a pregnancy test should be performed every 4 weeks. If a urine test is done and it is positive or cannot be confirmed as negative, a serum pregnancy test will be required.

7: Tumor assessments to be performed at (1) screening (PET scan may be within 42 days prior to C1D1) (2) within 0-24 days after completion of chemoradiation/prior to C1D1 of consolidation durvalumab, then every 3 months (about every 3 cycles/ $\pm$  7 business days) during consolidation durvalumab. Screening tumor assessment will consist of evaluation by CT scans of chest (contrast enhanced), PET scan, and contrast-enhanced MRI or CT of the brain. Response assessment imaging will include CT scans of chest, abdomen, and pelvis (contrast enhanced). MRI or CT brain or PET scan after screening should be performed as clinically indicated. Imaging selected for each subject should remain the same throughout the study. Tumor imaging at treatment discontinuation/D30 safety follow up visit is at discretion of site investigator. If tumor assessments are available for subjects who have not yet experienced progressive disease (PD) at the time treatment is discontinued, the follow-up tumor evaluations will be documented in the eCRF until PD or death is confirmed, or until another treatment is initiated. A window of 7 days may be applied to obtain scans.

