12: After the D100 safety visit, subjects who discontinue treatment for any reason without documented disease progression will be followed for disease progression every 3 months up to 12 months after initiation of consolidation durvalumab. Once disease progression is documented, subjects will enter a survival follow up period every 6 months for 1 year from the time of documented progression or until 1 year after initiation of consolidation durvalumab. Follow up may be accomplished via clinic visit, phone call, or other avenues as appropriate. A window of  $\pm$  14 days will be applied to follow up.

13: If screening (baseline) CBC and CMP were performed within 7 days of Day 1 of treatment, these do not need to be repeated. All laboratory assessments should be done prior to treatment.

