#### 9.8.8 Progression Free Survival

12-month progression-free survival will be measured using imaging prior to C1D1 consolidation durvalumab (between 1-42 days after completion of chemoradiation) as baseline. This timepoint is selected in order to compare with the PACIFIC trial 12-month progression-free survival as historical control. 12-month PFS will be defined as the time from the date of CT prior to beginning consolidation radiation until the date of objective disease progression or death (by any cause in the absence of progression), as measured for the 12-month period after initiation of consolidation durvalumab.

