#### 12.3 Sample Size and Accrual

This study will be planned to detect a 14% improvement in 12-month progression-free survival as a potential signal to move forward with further evaluation in a large randomized trial. Thus, 12-month progression-free survival of 69.9% would be felt to be clinically meaningful for further investigation.

Assuming that 12-month PFS in the historical control group is 55.9%, with an 18-month accrual interval and additional 12-month follow up after the accrual interval, the required sample size would be 49 patients, with a one-sided test given type I error 0.05 and power of 0.8.

Accounting for a 10% dropout rate, a total of 54 patients would be enrolled in this study.

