## 12.6 Data Analysis Plans

### 12.6.1 Analysis Plans for Primary Objective

The progression-free survival analyses will be performed considering the risk of dying from another cause before experiencing progression related events using the competing risk egression method (de Glas et al., 2016). Cumulative incidence functions will be displayed and summarized for the median time to progression as well as percentage of progression patients at 12, 18, and 24 months. In addition, competing risk regression will be used to estimate sub distribution hazard ratios of the study arm versus historical control arm and 95% confidence intervals, adjusted for patient demographic, clinical, pathological, and tumor related factors. To compare the overall survival between groups, Kaplan-Meier survival curves will be displayed and summarized. Survival curves will be statistically compared using the log-rank test. If the proportional hazards assumption is met, survival curves will also be compared using proportional Cox regression, adjusting for risk factors.

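### The 80% power stated for 49 patients is about 60–68% if the primary endpoint is confined to 12 months, and no test is named

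*Combined protocol and SAP*

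**What the plan says.** Section 12.3 plans to detect a rise in 12-month PFS from 55.9% to 69.9% and concludes that "the required sample size would be 49 patients, with a one-sided test given type I error 0.05 and power of 0.8". The calculation is made "with an 18-month accrual interval and additional 12-month follow up after the accrual interval"; the synopsis repeats it. Enrolment is set at 54 to allow for 10% dropout. No test or survival distribution is given.

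The documents differ on how long progression counts:

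- Section 9.8.8 defines PFS "as measured for the 12-month period after initiation of consolidation durvalumab". Sections 2.1.1, 2.2.1, 12.2.1 and 12.5 also name 12-month PFS as the endpoint.
- Section 7, footnote 12, has patients who stop treatment without progression "followed for disease progression every 3 months up to 12 months after initiation of consolidation durvalumab".
- The Section 7 calendar marks CT in the long-term follow-up column, headed "Every 3 months (±14days", with no end date in the table.
- Section 7, footnote 7, says of patients without progression when treatment stops, where assessments are available, that "the follow-up tumor evaluations will be documented in the eCRF until PD or death is confirmed, or until another treatment is initiated".
- Section 12.6.1 plans to report the "percentage of progression patients at 12, 18, and 24 months".

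For the primary objective, Section 12.6.1 plans competing-risk regression of the study arm against a historical control arm. It contains no one-sided test of 12-month PFS against 55.9%.

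**The concern.** A follow-up term of 18 months' accrual plus 12 more affects a sample size only if events after a patient's month 12 are used. If the endpoint stops at 12 months, that extra observation adds no information, and a sample size that relied on it is too small for the stated power.

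Section 12.3 presents the result as a possible signal for a large randomized trial. If real power is well below 80%, a regimen that truly reaches 69.9% is missed more often than the plan admits, and a negative result would be read as stronger evidence against it than 49 patients can give.

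**Working it through.** **Inputs (Section 12.3).** S0 = 0.559, S1 = 0.699, n = 49, one-sided α = 0.05 (z = 1.645), power 0.80 (z = 0.842), 18 months' accrual plus 12 months.

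**Assumptions not in the documents.** One-sample test, proportional hazards, uniform accrual, PFS clock running from accrual, no loss before month 12 and, at first, exponential PFS.

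**1. Hazards.** h0 = −ln(0.559)/12 = 0.04847 and h1 = −ln(0.699)/12 = 0.02984 per month; HR = 0.616.

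**2. Reproducing 49.** With follow-up uniform on 12 to 30 months, P(event) = 1 − (e^(−12h) − e^(−30h))/(18h), which is 0.627 under the null (P0) and 0.459 under the alternative (P1).

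- One-sample log-rank: n = (1.645√v0 + 0.842√v1)² / (v0 − v1)², with v1 = P1 = 0.459 and v0 = P1/HR = 0.746. This gives 48.25, rounded up to 49 (power at 49: 0.806).
- Exponential cube-root: n = [(1.645/√P0 + 0.842·HR^(1/3)/√P1) / (3(1 − HR^(1/3)))]², with HR^(1/3) = 0.851. This gives 48.98, also 49.

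That one of these was used is an inference. Other one-sample formulas on the same follow-up give, for example, 42.7, 46.8 and 57.3.

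**3. The same formulas stopped at 12 months.** P0 = 0.441 and P1 = 0.301, so v1 = 0.301 and v0 = 0.489. The log-rank formula needs 73.6 patients and the cube-root formula 71.3. A one-sample proportion needs 73.8 (normal) or 73.0 (arcsine). The exact binomial first reaches 0.80 at 79 patients and stays above it from 82. Expected events under the alternative fall from 49 × 0.459 = 22.5 to 49 × 0.301 = 14.7.

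**4. Power at 49 on 12-month data.**

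| Method | Actual α | Power |
|---|---|---|
| Exact binomial, at least 34 of 49 | 0.038 | 0.600 |
| Log-rank formula | nominal | 0.618 |
| Proportion, normal | nominal | 0.639 |
| Proportion, arcsine | nominal | 0.653 |
| Cube-root formula | nominal | 0.664 |
| Log-rank, simulated, null variance | 0.041 | 0.62 |
| Log-rank, simulated, averaged variance | 0.057 | 0.68 |

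With the simulated log-rank tests adjusted to a true α of 0.05, power is 0.65–0.66. With all 54 patients evaluable it is 0.65 (exact binomial, at least 37 of 54) to 0.71.

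**5. Effect detectable with 80% power at n = 49, 12-month data.** Cube-root 72.6%, arcsine 72.8%, normal 72.9%, log-rank 73.0%, exact binomial 73.6%.

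**6. If events after month 12 do count.** Under exponential PFS, simulated log-rank power is 0.77–0.81 when follow-up stops at 24 months and 0.78–0.82 when it is uncapped. But exponential PFS at 55.9% implies a control median of ln 2/0.04847 = 14.3 months, and Section 1.1 reports 16.8 for the same arm. A Weibull curve through both points (shape 0.52) gives 0.70–0.75 at 24 months and 0.71–0.76 uncapped, about 0.74 after size adjustment. It needs 58.1–58.7 patients uncapped. A piecewise-constant hazard through the same points (0.0485, then 0.0232 per month) also gives about 0.74.

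**The case against.** **The figure of 49 is not a slip of arithmetic.** It follows from the plan's inputs if all follow-up is used. This stands: the fault is that the calculation and the endpoint definition do not match, and the test is unnamed.

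**The 12-month limit is not certain.** Section 12.6.1 looks to 24 months, the calendar shows long-term CT, footnote 7 records later assessments, and footnote 12 covers only patients who stop treatment without progression. This also stands, and is why the 60–68% is conditional. The 36-month study duration in the synopsis does not settle it: it is also consistent with 18 months of accrual followed by induction, chemoradiation, a year of consolidation and safety follow-up.

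**The PFS clock starts after enrolment.** With an assumed 3.5-month lag, uncapped log-rank power is about 0.75 for analysis at month 30 and 0.84 at month 36. So the uncapped figure is sensitive to this choice. The 12-month figure hardly moves (0.607 for analysis at month 30).

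**The 0.74 rests on an assumed curve shape.** The documents give two points, not a curve, so this is a sensitivity result. It shows that 80% is not secure under longer follow-up, not what the power would be.

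**The range is soft.** The 0.68 comes from a test whose α exceeds 0.05, and other approximations run from about 0.575 to 0.693. A few poorly calibrated forms go further, to 0.56 and 0.77. None reaches 0.80.

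**This is a feasibility study with no stated no-go rule.** That limits the consequence but does not make the stated power correct.

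**Conclusion.** The concern holds, conditional on the horizon. If Section 9.8.8 governs, 49 evaluable patients give power of about 60–68% for 69.9% against 55.9% at one-sided 0.05, so the chance of missing that effect is 32–40% rather than 20%. Simulated tests that keep α at or below 0.05 without adjustment sit near 60–62%. All 54 evaluable would bring power to only 65–71%.

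If later events count, 80% is reached only under assumptions the plan does not state, and exponential PFS among them conflicts with the 16.8-month median in Section 1.1. These results assume a one-sample test, proportional hazards, uniform accrual and no censoring before month 12.

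Neither the stated 80% nor any figure here is the power of the competing-risk regression in Section 12.6.1.

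**What to change.** 1. Name the one-sample primary test against 55.9% in Section 12.3 and the synopsis, and carry it into Section 12.6.1.
2. State one progression horizon and reconcile it across Section 7 (long-term follow-up column, footnotes 7 and 12) and Sections 9.8.8, 12.3 and 12.6.1.
3. If the 12-month endpoint is kept, restate power at 49 evaluable patients with the exact figure for the named test (about 60–68%), or restate the 12-month PFS detectable with 80% power (about 73–74%). If an exact binomial is chosen, the text could read: *With 49 evaluable patients, success is at least 34 progression-free at 12 months (one-sided α 0.038); power is 60% at 69.9% and 80% at 73.6%.*
4. Do not justify 80% by longer scan follow-up alone. Section 9.8.8 would have to be redefined, and power is near 0.74 under the curves tried through the 16.8-month control median.

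The cost is a less favourable power statement or a larger stated detectable effect. It needs no added patients, visits or scans.

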#### 12.4 Assessment of Safety

All subjects receiving at least one dose of durvalumab will be evaluable for toxicity. The National Cancer Institute (NCI) Common Terminology Criteria for Adverse Events (CTCAE), version 5.0, will be used for toxicity grading. Please refer to the study calendar for the schedule of toxicity assessment.

#### 12.5 Assessment of Efficacy

All subjects who have received at least one dose of consolidation durvalumab and have their disease re-evaluated will be evaluable for the primary endpoint of 12-month PFS. In order to compare with the PACIFIC study as historical control, 12-month PFS will be measured starting at imaging performed 1-42 days after completion of chemoradiation, prior to initiation of consolidation durvalumab. See Section 12.6.1 for details regarding statistical analysis of the primary objective.

## 12.6 Data Analysis Plans

### 12.6.1 Analysis Plans for Primary Objective

The progression-free survival analyses will be performed considering the risk of dying from another cause before experiencing progression related events using the competing risk egression method (de Glas et al., 2016). Cumulative incidence functions will be displayed and summarized for the median time to progression as well as percentage of progression patients at 12, 18, and 24 months. In addition, competing risk regression will be used to estimate sub distribution hazard ratios of the study arm versus historical control arm and 95% confidence intervals, adjusted for patient demographic, clinical, pathological, and tumor related factors. To compare the overall survival between groups, Kaplan-Meier survival curves will be displayed and summarized. Survival curves will be statistically compared using the log-rank test. If the proportional hazards assumption is met, survival curves will also be compared using proportional Cox regression, adjusting for risk factors.

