### 12. STATISTICAL METHODS

#### 12.1 Study Design

This is a single arm study of induction durvalumab (1500 mg IV) for 1 cycle (every 4 weeks), administered prior to starting concurrent definitive chemoradiation, followed by consolidation durvalumab (1500 mg IV every 4 weeks) for up to 12 cycles.

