#### 12.2 Endpoints

##### 12.2.1 Definition of Primary Endpoint

1. Estimate 12-month progression-free survival (PFS) in patients with Stage III non-small cell lung cancer (NSCLC). Compare with PACIFIC trial 12-month progression-free survival as historical control. In the PACIFIC study, 12-month progression-free survival was 55.9% and was measured using baseline imaging from the time of patient randomization after completion of chemoradiation (1-42 days after completion of chemoradiation). For this study, in order to allow for comparison with this historical control, 12-month PFS will be measured starting at imaging performed 1-42 days after completion of chemoradiation, prior to initiation of consolidation durvalumab.
2. Assess the safety and feasibility of induction durvalumab followed by chemoradiation and consolidation durvalumab for stage III NSCLC. Toxicity will be measured and recorded as defined by the NCI Common Terminology Criteria for Adverse Events (NCI CTCAE) v5.

Patients receiving different chemotherapeutic agents will be analyzed together for toxicity, with exploratory analysis of toxicity related to different chemotherapeutic regimens.

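### Section 12.6.1 does not analyse the PFS endpoint defined in Section 9.8.8: death before progression becomes a competing risk, no patient-level control data are described, and no 12-month PFS estimator, test or threshold is named

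*Combined protocol and SAP*

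**What the plan says.** Section 12.2.1 sets the first primary aim: "Estimate 12-month progression-free survival (PFS) in patients with Stage III non-small cell lung cancer (NSCLC"), to be compared with the PACIFIC figure of 55.9%. Section 9.8.8 defines the endpoint as running "until the date of objective disease progression or death (by any cause in the absence of progression"), and "as measured for the 12-month period after initiation of consolidation durvalumab".

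Section 12.5 hands the analysis on: "See Section 12.6.1 for details regarding statistical analysis of the primary objective". Section 12.6.1 then states: "The progression-free survival analyses will be performed considering the risk of dying from another cause before experiencing progression related events". Its outputs are cumulative incidence functions "summarized for the median time to progression as well as percentage of progression patients at 12, 18, and 24 months". The comparison is by covariate-adjusted "sub distribution hazard ratios of the study arm versus historical control arm", with 95% confidence intervals. Kaplan-Meier, log-rank and Cox methods appear only for a between-group comparison of overall survival, which is not among the objectives in Section 2.1.

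Section 12.1 describes the design: "This is a single arm study of induction durvalumab". Section 12.3 (repeated in the Synopsis) gives the null of 55.9%, the target of 69.9%, one-sided type I error 0.05, power 0.8, 18 months of accrual plus 12 of follow-up, and 49 patients. It does not name the test.

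**The concern.** In a composite endpoint, death is one of the events. It cannot also be a competing risk for that endpoint. What Section 12.6.1 describes is an analysis of progression, a different quantity from PFS.

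The comparison has a separate gap. An adjusted subdistribution hazard ratio, a log-rank test or a Cox model between groups needs event times for control patients, and the adjusted models also need their covariates. The documents give PACIFIC's published summaries and describe no patient-level source.

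The result is meant to signal whether a large randomised trial should follow. If the estimator, test and threshold are unnamed, they can be chosen once the data are known.

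**Working it through.** **1. Definition against analysis**

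| | Section 9.8.8 | Section 12.6.1 |
|---|---|---|
| Death before progression | PFS event | competing risk |
| 12-month quantity | proportion alive and progression-free | percentage progressed |
| Comparator | PACIFIC 12-month PFS | historical arm, by adjusted regression |

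No estimator in Section 12.6 yields 12-month PFS.

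**2. Reproducing N = 49**

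Inputs from Section 12.3: S0 = 0.559, S1 = 0.699, one-sided 0.05 (z = 1.645), power 0.80 (z = 0.842), 18 + 12 months.

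- Exponential hazards: λ0 = −ln(0.559)/12 = 0.0485; λ1 = −ln(0.699)/12 = 0.0298; ratio 0.616.
- Event probability with uniform accrual: P = 1 − (e^(−12λ) − e^(−30λ))/(18λ), giving 0.627 under the null and 0.459 under the alternative.
- One-sample exponential test on the cube root of the hazard, c = λ^(1/3): n = [1.645·c0/(3√0.627) + 0.842·c1/(3√0.459)]² / (c0 − c1)² = 48.98, so 49.

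The plan's figure therefore reproduces with a test on all follow-up. Related full-follow-up variants have power of 0.77 to 0.82 at 49. Section 12.6.1 contains no such test.

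**3. The same 49 patients with a 12-month test**

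- Exact binomial: P(X ≥ 34 | 49, 0.559) = 0.038 and P(X ≥ 33) = 0.069, so the cut-off is 34. Power P(X ≥ 34 | 49, 0.699) = 0.600.
- Kaplan-Meier log-log lower limit without censoring: S^exp(1.645·se), with se = √[(1 − S)/(nS)]/|ln S|. For 34/49 (S = 0.694, se = 0.260) the limit is 57.1%. For 33/49 (S = 0.673, se = 0.252) it is 55.0%. Only the first exceeds 55.9%, so the cut-off is the same; simulated type I error is 0.037 and power 0.599.
- Normal approximation: power 0.64.
- One-sample log-rank cut at 12 months: 0.61 to 0.68.
- Exponential test cut at 12 months: 0.66 to 0.69.

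For 0.80 with a 12-month proportion, n = [1.645√(0.559·0.441) + 0.842√(0.699·0.301)]²/0.14² = 73.8, so 74. The exact test with at least 52/79 has power 0.82.

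**4. How safe is the full-follow-up test?**

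- Its null median is ln 2/0.0485 = 14.3 months, against 16.8 months for durvalumab in Section 1.1. The null curve gives 44.3% at 16.8 months instead of 50%.
- If the null really is exponential, simulated type I error is 0.042 to 0.054, depending on the variance form.
- A curve through both PACIFIC figures has hazard ln(0.559/0.5)/4.8 = 0.0232 per month from 12 to 16.8 months. If that hazard continues, type I error is 0.243 to 0.280. If it returns to 0.0485, it is 0.112 to 0.137. Both continuations are assumptions.

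**5. Follow-up and time zero**

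- Twelve cycles of 28 days end at day 336 (11.0 months). The last dose falls at about day 11 × 28 = 308, and the day-100 safety visit at about day 408 (13.4 months).
- Footnote 12 of the study calendar starts progression follow-up after that visit but ends it 12 months after consolidation began. For patients completing 12 cycles the window is empty. Footnote 7 leaves imaging at discontinuation or day 30 to the site investigator.
- Section 2.1.1 starts the clock at consolidation durvalumab. Sections 12.2.1 and 12.5 start it at imaging 1-42 days after chemoradiation. Section 9.8.8 starts it at the CT before consolidation radiation, apparently a slip for durvalumab.

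**6. Illustration only**

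If a share f of 12-month failures were deaths without progression, and 1 minus cumulative incidence were read as PFS, a true 55.9% would read 1 − 0.441(1 − f). That is 58.1%, 60.3% or 64.7% for f = 5%, 10% or 20%. Under the 34/49 rule the false-positive rate would be 7.1%, 12.4% or 30.1% instead of 3.8%. The documents give no value for f.

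**The case against.** **The design parameters are fixed in advance.** True: null, target, alpha and power all stand in Section 12.3. The gap is narrower, namely the PFS estimator, the test statistic and the decision threshold.

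**N = 49 is correct.** A reader might infer from the 0.60 that the sample size is wrong. The documents do not support that: 49 reproduces under a full-follow-up test, and Section 12.3 names no 12-month landmark test. The lower power belongs to the 12-month test, if that is chosen.

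**The regression handles deaths alike in both groups.** A reader might infer that the plan will flatter the new regimen. It would do so only if 1 minus cumulative incidence were set beside 55.9%. No passage plans this, and the shares of deaths without progression are assumed. Section 12.6.1 also speaks of dying from another cause, which may be narrower than all deaths before progression. The conflict remains because Section 9.8.8 counts death from any cause.

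**A historical arm is not a concurrent arm.** A reader might conclude that the comparison is impossible. The documents show only that no control dataset is described; naming one would answer this part.

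**The full-follow-up test keeps 0.80.** It does, and nothing here rules it out. The inflated error rates need assumed later hazards. But its null does not match the published median, and the progression follow-up it relies on may not be collected after 12 months.

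**Conclusion.** The point stands and should be corrected before analysis. Section 12.6.1 contradicts Section 9.8.8 on whether death is an event. Followed as written, the plan yields no estimate of 12-month PFS and no test of it against 55.9%. This rests on the text alone and needs no assumption.

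The practical size lies in the unnamed test: power at 49 is about 0.80 with an exponential-type test on all 18 + 12 months, and about 0.60 to 0.69 with a 12-month test. The first figure assumes exponential PFS and progression follow-up beyond 12 months. The equivalence of the log-log rule with 34/49 assumes complete 12-month status, which the study calendar does not clearly secure for patients completing 12 cycles. The bias figures are illustrative and are no part of the conclusion.

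**What to change.** 1. In Section 12.6.1, define a PFS event as progression or death from any cause, and state one time zero. Reconcile Sections 2.1.1, 9.8.8, 12.2.1 and 12.5 with it.
2. Estimate 12-month PFS by Kaplan-Meier with a log-log confidence interval. Declare a signal if the one-sided 95% lower limit exceeds 55.9%. With complete status in 49 patients this means at least 34 event-free.
3. Make the power statement in Section 12.3 match the chosen test. With the 12-month rule above, state about 0.60 at N = 49 and enrol no more patients. If a full-follow-up test is preferred, justify its null curve and secure the follow-up it needs.
4. Keep cumulative incidence of progression as descriptive. Report overall survival as a single-arm Kaplan-Meier curve. Drop the historical-arm regression and the between-group tests unless a patient-level control source is named.
5. Reconcile footnotes 7, 11 and 12 of the study calendar with the 12-month endpoint, including how 12-month disease status is established for patients completing 12 cycles, and with the 18- and 24-month summaries.

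Items 1 to 4 change text only. Their downside is a less favourable stated power if the 12-month test is used. Item 5 is also text, unless it shows that 12-month status needs an assessment not now required.
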